#### 4.3.2. Predicted Efficacious Dose

An *in-situ* binding assay was used to characterize GSK3882347 mediated inhibition of UPEC binding to healthy or inflamed human bladder epithelium. Although there was much variation in the level of binding by the strains to human bladder tissue- either healthy or inflamed, all strains tested could be inhibited by GSK3882347 and in the clear majority of cases tissue binding was inhibited by >95% at 30 µM (or less), relative to vehicle controls. *In vivo* efficacy studies were also completed using the acute therapeutic model in mice with UPEC strain UTI89 to correlate microbiological efficacy and urinary exposure. A preliminary PK/PD target for GSK3882347 was determined as the maintenance of a trough concentration of ≥5 µM in urine for the duration of the dosing period. Importantly, achieving this target provided maximal efficacy regardless of dosing

regimen (regimens evaluated: QD, BID, and TID). Based on the studies described above, a target Cmin concentration range of 5-30  $\mu$ M was defined to support dose selection in this study.

The predicted efficacious doses for humans were calculated using the PBPK model based on the target urine Cmin range of 5-30  $\mu$ M at day 1 and considering the difference in the rat and dog pharmacokinetics (see [Table 7](#)).

**Table 7 Anticipated Therapeutic Dose Range Considering Different Target Urine Cmin and Human Predicted Pharmacokinetics Based on Rat and Dog Pre-clinical Data**

Predicted Human Therapeutic Dose		
Urine target C min ( $\mu$ M)	Based on Dog PK	Based on Rat PK
5	50 mg	300 mg
30	300 mg	650 mg

#### 4.3.3. Food Effect

The dose of GSK3882347 to be administered will be determined from Part 1 to ensure an adequate safety margin assuming an arbitrary two-fold increase in exposure to GSK3882347 when administered with food.

#### 4.3.4. Part 2: Starting Dose and Dose Escalation

Four dose levels are planned, with escalation increments no greater than 3.5-fold. The lowest dose is expected to be 50 mg. The highest dose will not exceed the top dose tested in Part 1. Doses and dosing regimen will be based on findings from Part 1 and emerging observations in Part 2.

#### 4.4. End of Study Definition

A participant is considered to have completed the study if he/she has completed all phases of the study including the last visit.

The end of the study is defined as the date of the last visit of the last participant in the study.

## 5. STUDY POPULATION

Prospective approval of protocol deviations to recruitment and enrollment criteria, also known as protocol waivers or exemptions, is not permitted.

### 5.1. Inclusion Criteria

Participants are eligible to be included in the study only if all the following criteria apply:

#### Age

1. Participant must be 18 to 50 years of age inclusive, at the time of signing the informed consent.

#### Type of Participant and Disease Characteristics

2. Participants who are overtly healthy as determined by medical evaluation including medical history, physical examination, laboratory tests, and cardiac monitoring. A participant with a clinical abnormality or laboratory parameter(s) not specifically listed in the exclusion or exclusion criteria that is outside the reference range for the population being studied may be included only if the investigator, in consultation with the Medical Monitor (if required), agree and document that the finding is unlikely to introduce additional risk factors and will not interfere with the study procedures.

#### Weight

3. Body weight at least 50.0 kg (110 lbs.) for males and 45.0 kg (99 lbs.) for females; and body mass index (BMI) within the range 18.5 – 32.0 kg/m^2 (inclusive).

#### Sex

4. Male and female participants

- Female Participants:

A female participant is eligible to participate if she is of non-childbearing potential as defined in [Appendix 4](#)

- Male Participants:

Male participants are eligible to participate if they agree to the following during the intervention period for at least five days, corresponding to time needed to eliminate study intervention(s) (e.g. 5 terminal half-lives) after the last dose of study intervention:

- Refrain from donating sperm

PLUS either:

- Be abstinent from heterosexual or homosexual intercourse as their preferred and usual lifestyle (abstinent on a long term and persistent basis) and agree to remain abstinent

OR

- Must agree to use contraception/barrier as detailed below
  - Agree to use a male condom and should also be advised of the benefit for a female partner to use a highly effective method of contraception (see [Appendix 4](#)) as a condom may break or leak when having sexual intercourse with a woman of childbearing potential who is not currently pregnant.

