## Part 2: Repeat Dose Escalation in Healthy Adult Participants

Part 2 consists of a maximum of four ascending repeat-dose cohorts (Cohorts 3 to 6), each with 10 participants who will receive a single oral dose of GSK3882347 or placebo for 7 days. The earliest point at which Part 2 of the study will be initiated is once the single dose safety and preliminary PK data at an exposure that exceeds the daily exposure predicted at steady state for the Part 2 planned starting dose of 50 mg is demonstrated in Part 1. The planned starting dose of GSK3882347 in Part 2 is 50 mg administered as once daily Days 1 to Day 7. The dose is planned to increase in subsequent cohorts to 150, 500 and 900 mg. The starting dose and maximum dose may be changed based on clinical safety, tolerability and PK findings in Part 1 or earlier doses in Part 2 and consideration of the area under the concentration-time curve (AUC) from time zero to 24 hours after dosing (AUC[0-24]) and maximum plasma concentration (Cmax) exposures based on the no-observed-adverse-effect-level (NOAEL).

Participants who meet the criteria for study entry will be assigned to the current dose level and randomized to receive GSK3882347 or placebo in a 4:1 ratio before administration of study intervention on Day 1 in Part 2. As a safety precaution, cohorts will be split into two sub-cohorts to allow sentinel dosing. At each dose level (Cohorts 3-6), the first two participants will receive either GSK3882347 or placebo (one active and one placebo). Dosing of the remaining eight participants (seven active and one placebo) in that cohort will occur at least 120 hours later based on review of the safety data (e.g. vital signs, ECGs, clinical laboratory results and adverse events) by the Principal Investigator and sponsor Medical Monitor from all sub-cohorts of sentinel participants. The 120 hour timeframe was selected on the basis of available preclinical data, as GSK3882347 is anticipated to have reached steady-state by 120 hours, however this duration may be increased or decreased based on emerging PK data.

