Doses are planned to escalate in a sequential fashion contingent on the preliminary safety, tolerability and pharmacokinetic data from Part 1 and at least 7 days of repeat dosing in a minimum of five participants who received active treatment in the previous cohort in Part 2. The dosing frequency, duration of dosing, and decision to dose (escalations or reductions) in the next dose level may be changed based on the safety, tolerability or pharmacokinetic findings in Part 1 or earlier doses in Part 2.

[figure not shown]
Continuous ECG recording will be performed on Day 1 and Day 7 for extraction of ECGs paired with PK sampling.

In Part 2, participants will remain in the clinical unit from admission on Day-1 until after all scheduled safety and pharmacokinetic assessments have been completed (approximately 5 days post the last dose or 5 half-lives, whichever is longer based on the emerging data from Part 1). The duration of study participation will be up to approximately 8 weeks (~30 days screening, up to 12 days in-house assessment period, and ~14-days follow-up period).

**Dose Escalation Committee:** Yes

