## 4. STUDY DESIGN

### 4.1. Overall Design

This is a two-part phase I, FTIH, randomized, double-blind, single-center, placebo-controlled, dose-escalation study to determine the safety, tolerability and pharmacokinetics of GSK3882347 following oral administration of single (Part 1) and repeat doses (Part 2) in healthy adult men and WONCBP. Part 1 will consist of two cohorts with a maximum of four-period cross-over. The food effect evaluation will be conducted in the last period (Period 4) in only one of the cohorts based on the observed human pharmacokinetics.

During Parts 1 and 2, participants who meet the criteria for study entry will be assigned to the current dose level and randomized to receive GSK3882347 or placebo before administration of study intervention on Day 1.

Dose escalation will be conducted only if it is supported by safety, tolerability and pharmacokinetic results from the preceding dose level(s). This is the first administration of GSK3882347 in humans; therefore, preliminary safety, tolerability and pharmacokinetic results will be reviewed internally at GSK in conjunction with the study site and study design adjustments may be made based on emerging data from each dose cohort. The repeat dose escalation component (Part 2) of this study will be initiated once safety at an exposure that exceeds the daily exposure predicted at steady state for the Part 2 planned starting dose of 50 mg has been demonstrated in Part 1. This is predicted to occur at the 250 mg single dose. The point at which Part 2 is initiated can be modified based on the emerging safety, tolerability and pharmacokinetic data from Part 1.

In Part 1, participants will remain in the clinical unit from admission on Day-1 until all scheduled safety and pharmacokinetic assessments have been completed for that dose (approximately 5 days) for each period. The duration of study participation will be approximately 3 months (~30 days screening, 5 days in-house assessment for the

completion of a maximum of the four periods, 2 weeks between each dose escalation and ~14-day follow-up period) for completion of up to four periods. Part 1 will consist of two cohorts with up to a four-period cross-over. The food effect evaluation will be conducted in last period (Period 4) in only one of the cohorts based on the observed human pharmacokinetics.

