In Part 2, participants will remain in the clinical unit from admission on Day-1 until after all scheduled safety and pharmacokinetic assessments have been completed (approximately 5 days post the last dose or 5 half-lives, whichever is longer based on the emerging data from Part 1). The duration of study participation will be up to approximately 8 weeks (~30 days screening, up to 12 days in-house assessment period, and ~14-days follow-up period).

Study schematic is provided in [Figure 1](#).

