#### **4.3. Justification for Dose**

Estimated human pharmacokinetics for GSK3882347 were generated using a physiologically based pharmacokinetic (PBPK) model that correlates plasma and urine exposures incorporating estimates of renal and non-renal clearance derived from single species scaling of observed *in vivo* male rat and dog data. The predicted human clearance of GSK3882347 using rat or dog data differed by approximately 10-fold, therefore, two separate predictions of likely human pharmacokinetics and exposure for GSK3882347 in plasma and urine were established for a 70 kg human.

The highest planned dose in this study is 900 mg, which, for the human exposure prediction based on dog PK, provides 1.8-fold coverage to the rat NOAEL, when dosed

once-daily repeat doses. The doses in the protocol may be amended based on emerging human safety and PK data, however the human exposure will remain below the rat NOAEL and ICHQ3 principles will be followed to ensure that any impurities present in the drug product remain at acceptable levels if dose levels above 900 mg are used.

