### **8.3.5. Pregnancy**

- Details of all pregnancies in female partners of male participants will be collected where conception may have occurred during or up to 5 days after dosing.
- If a pregnancy is reported, the investigator should inform GSK within 24 hours of learning of the pregnancy and should follow the procedures outlined in [Appendix 4](#).
- Abnormal pregnancy outcomes (e.g., spontaneous abortion, fetal death, stillbirth, congenital anomalies, ectopic pregnancy) are considered SAEs.

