#### **8.5.2. Urine Sample Collection**

- Urine samples will be collected up to 96 hours from dosing in Part 1 and up to 24 hours from dosing on Days 1 and 7 in Part 2 MAD (exact times are specified in the SoA). The time will be recorded for each urine sample collected, and the total urine volume for each subject will be recorded over the collection time period.
- From each urine PK interval, a 1 mL aliquot of urine will be collected for PK analysis and stored at approximately 70°C or colder. **Note: it is highly important that the urine sample is thoroughly mixed using several repeat inversions of the sample prior to removal of the 1 mL aliquot for PK analysis.**
- The metabolite profiling of the urine samples will be conducted under separate protocols and results are reported separately according to the IV/IVT DMPK, GSK protocols.
- The timing of urine samples may be altered and/or samples may be obtained at additional time points to ensure thorough PK monitoring.

Details of urine sample processing, storage and shipping procedures are provided in the SRM.

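### Criterion 4 ties a five-day minimum for male contraception to 5 terminal half-lives but lacks the 'whichever is longer' trigger that the Part 2 stay rule uses for the same unknown half-life

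*Protocol*

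**What the plan says.** Inclusion criterion 4 (section 5.1, Sex) binds men during the intervention period and then "for at least five days, corresponding to time needed to eliminate study intervention(s) (e.g. 5 terminal half-lives) after the last dose". Five days is a floor, and the half-life phrase explains where it comes from. Section 8.3.5 collects partner pregnancies "where conception may have occurred during or up to 5 days after dosing".

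Elsewhere the protocol treats elimination time as something still to be learned:

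- Section 4.1 sets the Part 2 stay at "approximately 5 days post the last dose or 5 half-lives, whichever is longer based on the emerging data from Part 1".
- The synopsis (1.1, Part 2) says of the sentinel interval that the drug is "anticipated to have reached steady-state by 120 hours, however this duration may be increased or decreased based on emerging PK data".
- Section 4.3 says that "predicted human clearance of GSK3882347 using rat or dog data differed by approximately 10-fold".
- No human half-life is stated; section 3 lists it as a Part 1 endpoint.

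In Part 1 the stay has no half-life arm. Participants remain "until all scheduled safety and pharmacokinetic assessments have been completed for that dose (approximately 5 days) for each period" (section 4.1), and section 8.5.2 states: "Urine samples will be collected up to 96 hours from dosing in Part 1".

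**The concern.** Criterion 4 equates a fixed number of days with a multiple of a quantity that has not yet been measured in humans. If Part 1 shows a half-life above 24 h, a man can meet the stated minimum before 5 half-lives have passed, and nothing in the criterion prompts the site to lengthen the period. Section 4.1 has exactly that prompt for the Part 2 stay.

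The exposure is narrow. Part 2 men remain in the unit under the longer-of rule. In Part 1, men are still within the intervention period between doses, so the gap opens only after the final dose. At that point a man leaves at about 96 h, so the last 24 h of the five-day floor, and any time beyond it, are spent at home.

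**Working it through.** **1. The protocol's own equivalence.** Five days = 5 × 24 = 120 h. Five half-lives fit within 120 h only if t½ ≤ 120 / 5 = 24 h.

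**2. What the predictions imply.** Tables 5 and 6 (section 4.3.1) give predicted AUC(0-24) and Cmax after a single dose and at steady state, and these carry information about the half-life. The model is an assumption, not the protocol's PBPK model: one compartment, first-order absorption (rate ka), elimination rate ke, scale S = F × dose / V, dosing every 24 h.

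- Single dose: C(t) = S·ka/(ka − ke) · (e^(−ke·t) − e^(−ka·t)).
- AUC(0-24) = S·ka/(ka − ke) · [(1 − e^(−24ke))/ke − (1 − e^(−24ka))/ka].
- Cmax is C(t) at t = ln(ka/ke)/(ka − ke).
- Steady state: AUC = S/ke. For Cmax, each e^(−kt) is divided by (1 − e^(−24k)) and the maximum taken over 24 h.
- t½ = ln 2 / ke.

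For each dose, ka, ke and S were fitted by least squares on logs to the four tabulated values.

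| Dog-based, Table 5 | Single AUC, Cmax | Steady-state AUC, Cmax | ka (/h) | t½ (h) | 5 × t½ (h) |
|---|---|---|---|---|---|
| 50 mg | 4.00, 0.20 | 8.87, 0.43 | 0.29 | 23.7 | 118 |
| 150 mg | 11.8, 0.60 | 26.5, 1.28 | 0.30 | 23.8 | 119 |
| 500 mg | 32.0, 1.60 | 80.0, 3.70 | 0.18 | 24.5 | 123 |
| 900 mg | 40.5, 1.94 | 107, 4.97 | 0.26 | 29.7 | 149 (not relied on) |

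Check at 50 mg: ke = 0.693/23.66 = 0.0293, ka = 0.287, S = 0.260, so the leading factor is 0.290. Single-dose AUC(0-24) = 0.290 × (17.24 − 3.48) = 3.99, against 4.00 in Table 5.

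**3. How firm these values are.** At 50, 150 and 500 mg, the half-lives that reproduce all four entries within 2% give 5 × t½ of 99 to 128, 96 to 130 and 91 to 144 h. At 900 mg, fixing t½ at 24 h (ka 0.13/h) still reproduces all four entries within 3.8%. One half-life shared across all four doses fits at 24.6 h (5 × = 123 h), with every entry within 3.5%. The 900 mg best fit is therefore poorly identified.

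**4. Rat-based predictions, Table 6.** The same fit gives 5 × t½ = 12.5, 12.9, 22.5 and 33.6 h at 50, 150, 500 and 900 mg. With absorption treated as instantaneous, the values are 19.1, 19.1, 24.5 and 34.8 h. All lie far below 120 h.

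**5. What remains at 120 h.** The fraction is 2^(−120/t½): 3.1% at t½ = 24 h (by definition, 5 half-lives) and 6.3% at 30 h.

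**The case against.** The best defence is that nothing in criterion 4 is miscalculated. It sets a minimum linked to a purpose, much as section 8.4 does for overdose monitoring, and the planning data support it: the dog-based fit sits almost exactly on 120 h and the rat-based one far below. The synopsis separately anticipates steady state by 120 h. By a man's last Part 1 dose, earlier-period PK will usually have been reviewed, and assessment timing may be changed on emerging data. The document also describes no semen-mediated hazard. All of this stands, and it limits the point to a missing trigger.

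Three stronger readings are tempting but not supported:

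- *The dog-based predictions already put 5 half-lives at 139 to 175 h.* That comes from the simple accumulation ratio, for example R = 107/40.5 = 2.64 at 900 mg, with t½ = 24·ln 2 / (−ln(1 − 1/R)) = 35.0 h. It treats absorption as instantaneous, so it overstates the half-life of an oral drug. The 149 h absorption fit at 900 mg is no firmer: steady-state AUC rises 107/8.87 = 12.1-fold for an 18-fold dose, and section 4.2 reports limited fasted solubility. Both suggest slow or incomplete absorption, which this model can mistake for slow elimination.
- *Partner pregnancies conceived after day 5 would be lost.* Section 10.4.3 already seeks information on partners who become pregnant during participation.
- *The phrase "up to 12 days in-house assessment period" contradicts the longer-of stay rule.* It belongs to an approximate duration estimate, and the discharge rule stands in the same paragraph.

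What the defence does not supply is an instruction to extend the period. A man agrees to a stated minimum, and the half-life phrase reads as the reason for five days, not as an alternative limit.

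**Conclusion.** The point holds as a consistency and safety improvement, not as an arithmetic error. The break-even half-life is 24 h. On the rat-based predictions nothing is lost. On the dog-based ones, five days match 5 half-lives at 50 to 500 mg with no margin (118 to 123 h against 120 h), so a modest upward departure in humans would break the equivalence. These figures assume a one-compartment model with first-order absorption fitted to rounded predictions; the 24 h threshold and the missing trigger do not depend on that model. The practical effect is confined mainly to the days after a man's final Part 1 dose. No endpoint, sample size or escalation decision is affected, and the documents do not allow the reproductive consequence to be quantified.

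**What to change.** In criterion 4 write: *at least five days or 5 terminal half-lives based on emerging Part 1 data, whichever is longer, after the last dose*. Use the same wording in section 8.3.5, where it is alignment only. At the first dose level, before any human half-life is known, the five-day floor simply stands. The half-life is already a Part 1 endpoint with sampling to 96 h, so no new data are needed.

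The cost is amendment and consent wording and, only if the observed half-life exceeds 24 h, possibly a few extra days of condom use and no sperm donation. At a half-life of 30 h, for example, the period becomes 150 h, or 6.25 days. The stated in-house duration needs no change.

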### **Informed Consent**

5. Capable of giving signed informed consent as described in [Appendix 1](#) which includes compliance with the requirements and restrictions listed in the ICF and in this protocol.

### **5.2. Exclusion Criteria**

Participants are excluded from the study if any of the following criteria apply:

#### **Medical Conditions**

1. History or presence of cardiovascular, respiratory, hepatic, urological, gastrointestinal, endocrine, haematological, or neurological disorders capable of significantly altering the absorption, metabolism, or elimination of drugs; constituting a risk when taking the study intervention; or interfering with the interpretation of data.
2. Alanine transaminase (ALT)  $>1.5 \times$  upper limit of normal (ULN)
3. Bilirubin  $>1.5 \times$ ULN (isolated bilirubin  $>1.5 \times$ ULN is acceptable if bilirubin is fractionated and direct bilirubin is  $<35\%$ )
4. Current or chronic history of liver disease or known hepatic or biliary abnormalities (except for Gilbert's syndrome or asymptomatic gallstones).
5. Medical history of cardiac arrhythmias or cardiac disease or a family or personal history of long QT syndrome.
6. Exclusion criteria for screening ECG:

	Males	Females
Heart rate	$<45$ or $>100$ bpm	$<50$ or $>100$ bpm
PR Interval	$<120$ or $>220$ msec	
QRS duration	$<70$ or $>120$ msec	
QTcF interval		$>450$ msec

*Notes: A heart rate from 100 to 110 bpm can be rechecked by ECG or vitals within 30 minutes to verify eligibility, and the second reading used if this falls within acceptable limits.*

*The QTc is the QT interval corrected for heart rate according to Fridericia's formula (QTcF).*

7. Evidence of previous myocardial infarction on ECG (does not include ST segment changes associated with re-polarization).
8. Any conduction abnormality (including but not specific to left or right complete bundle branch block, AV block [2nd degree or higher], WPW syndrome).
9. Sinus Pauses >3 seconds
10. Any significant arrhythmia which, in the opinion of the Investigator or GSK Medical Monitor, will interfere with the safety for the individual participant.
11. Non-sustained or sustained ventricular tachycardia (3 consecutive ventricular ectopic beats).
12. Current or history of renal disease, or estimated creatinine clearance <90 mL/min/1.73m^2 or serum creatinine >ULN at screening.

### **Prior/Concomitant Therapy**

13. Unable to refrain from the use of prescription or non-prescription drugs, including vitamins, herbal and dietary supplements (including St John's Wort) within 7 days (or 14 days if the drug is a potential enzyme inducer) or 5 half-lives (whichever is longer) before the first dose of study intervention, unless in the opinion of the Investigator and the GSK medical monitor, the medication will not interfere with the study procedures or compromise participant safety.
14. Use of a systemic antimicrobial within 30 days of screening.

